10.4.2.8 Gut microbiome

There is increasing evidence that dynamic changes within the microbiome can affect both immune and cancer cells. Imbalance in microbial communities promotes chronic inflammation and predisposes to cancer (Garett, 2015). Our collaborators have shown that microbiome is also involved in the metabolism of drugs and could explain person-to-person variability and responsiveness to therapy (Alexander *et al*, 2017, Zimmermann *et al*, 2019). Unlike in several

solid tumors wherein, immune-check point blockade is used alone or in combination or with cytotoxic agents, the drug synergism to treat AML is unique. Majority of these combinations results in mucositis which helps microbes breach gastro-intestinal (GI) epithelial barrier. It is plausible that with each cycle of treatment, exposure of immune cells to time -prevalent oral and GI microbiome is subject to temporal variance. Extrapolating preclinical data, taxonomically unique microbes could further determine priming of antigen presenting cell interaction with immune-effector cells that ultimately determine clinical phenotype. Based on our current understanding on the mechanism of action of PD-1 inhibitors, our overall hypothesis is that gastro-intestinal microbiome holds salutary prognostic and therapeutic promise in patients with AML. Our preliminary hypothesis is that gut microbiome modulates clinical responses and toxicity in patients with AML receiving Check Point Inhibitors (CPI). To this end our proposal will test the longitudinal relationships between the taxonomy and diversity of gut microbiome and metabolite on clinical outcomes and toxicity.

Analysis of microbiome communities will be performed in R (<http://www.R-project.org>), using phyloseq²⁷ to calculate α - and β - diversity metrics. The Shannon Diversity Index (SDI) will be used for α -diversity (variance within a particular sample; a measure of bacterial diversity) metric calculations, and weighted and unweighted UniFrac for β -diversity distances (characterization of differences in microbial community composition; a measure of temporal stability of the microbial community structure).²⁸ Temporal variability will be determined using coefficients of variation (CV) [a measure of stability of species diversity over time] of the SDI and unweighted and weighted UniFrac distances per patient, with higher values indicative of more variable community composition. Pairwise differences in temporal variability across body sites will be made using Mann–Whitney U test, whereas pairwise differences among response groups performed using Student’s t-test. Linear correlations between CVs will be determined using Pearson’s r correlation. The population cohort will be divided into quartiles based on CV of the weighted UniFrac distance values or SDI where the first quartile is defined as stable, second and third as average, and fourth as variable. Measurements of intra-patient temporal variability and patient stability categories will be analyzed for their correlations with genera abundances. Groups of patients will be analyzed to determine if patients with subsequent clinical outcomes had significantly different levels of microbiome temporal variability. Potential clinical drivers of microbiome temporal instability will be determined using multivariable regression analyses. Untargeted metabolite analyses from stool samples with mass spectroscopy will be performed.

The primary outcome of interest is to longitudinally characterize microbial shifts in patients with AML receiving PD-1 inhibitors. For this analysis standard of care will be compared with the experimental arm which includes chemotherapy + Pembrolizumab (MK-3475) combination. Secondary outcomes of interest will be a measure of both efficacy and toxicity which will include variables like rates of CR/CRi, progression free survival (PFS), overall survival (OS), cumulative incidence of graft versus host disease (GVHD)/non-relapse mortality (NRM). Association between microbial diversity on the percentage of patients with minimal residual disease (MRD) negative complete remission (CR) (MRD-CR) as measured by flow cytometry at the end of first consolidation cycle will also be explored.

Exploratory outcomes:

Correlation between microbial/metabolome changes with immune-checkpoint expression and kinetics of immune cell subset recovery and programming in the standard of care and experimental arm will be evaluated. As a marker of mucosal immunity, changes in immune cell content within stool samples in patients that experience colitis or GI-GVHD will be compared to suitable controls.

Part 1: Assess whether baseline biomarkers or the serial measurements of biomarkers are associated with response outcomes.

A univariate logistic regression will be selected to assess baseline biomarkers associated with response outcomes. The dynamic changes of PD-L1/ PD-1 expressions, concentration of cytokine, RNA seq/TCRseq, gut microbiome, etc. will be monitored. The measurements of biomarkers in changes over time from baseline to several time-points will be performed by using generalized linear mixed effects modeling with a Benjamini-Hochberg correction (Benjamini *et al.*, 1995) to control for false discovery rate.

Part 2: Assess whether baseline biomarkers or the serial measurements of biomarkers are associated with survival outcomes.

The Kaplan-Meier method and log-rank test will be used to estimate the distribution of survival between/among different marker strata. Univariate or Multivariate cox proportional hazard models will be employed to explore the significance of biomarkers on survival outcomes, while adjusting for the potential prognostic factors. The interaction effects between treatment and biomarkers also will be evaluated. Serial measurements of biomarkers will be estimated at baseline, end of induction, post-consolidation cycle 1 and 4, every 3 months during maintenance, one year, and end of treatment when applicable. Landmark analysis (Benjamini *et al.*, 1995, Dafni *et al.*, 2011) or joint modeling (Huang *et al.*, 2016) will be used to assess serial measurements of biomarkers dynamical impacts on survival outcomes, where appropriate.

Part 3: Compare the biomarkers effects between treatment arms, intensive chemo + pembro vs. intensive chemo only.

The associations between treatment arms and baseline biomarkers will be evaluated using Chi-squared test/ Fisher's exact test, ANOVA, and the Mann-Whitney U tests as appropriate. Trajectory trends of the changes in markers' values or status across the measurement time will be explored using generalized linear mixed models. The bar plots and trajectory time plots will visually show the differences over time between treatment arms. The associations between markers and the demographic/prognostic factors will also be assessed using the similar statistical methods.

Part 4: Evaluate the correlations between biomarkers.

The correlations between biomarkers will be evaluated using Pearson/Spearman rank-order correlation coefficients, Chi-squared/Fisher's exact tests, and Wilcoxon rank sum / Kruskal-Wallis tests as appropriate. A scatter plot, boxplot, and mosaic plot will also be generated for visualization. The multiplicity of the endpoints will be adjusted using the correction of Benjamini and Hochberg (Benjamini *et al.*, 1995).

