5.4.6 Collection of Stool in OMNIgene-GUT Tubes for Shipment to the EET Biobank

Baseline and “Consolidation therapy phase – Post Cycle 1” timepoints will use OMNIgene GUT kits (OMR-200.100—shipped ambient) which include a DNA stabilizing solution. Collection kits will include directions for specimen collection and shipment as well as collection and shipping supplies.

1. Clinical site staff will explain to patients how to use the kits at the clinic or in the privacy of their home. The collection tube must be labeled by clinical site staff according to instructions in 5.3.2 prior to being provided to the patient.
2. The patient will collect the stool sample and return the sample to the site staff. It is recommended that patients return the specimens within 24 hours, when collected at home. The stool specimen should be kept ambient until shipment.
3. The stool and a shipping manifest should be shipped on day of collection (whenever possible) according to instructions provided in the kit and section 5.5.1.2.
4. Collection site staff should not ship any samples that do not utilize the collection kit properly.

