7.1.1 Induction therapy phase

Eligible patients will be randomized before proceeding to 7+3, or within one week of starting 7+3 in 1:1 ratio, to 7+3 alone or 7+3+ Pembrolizumab (MK-3475). As shipment of pembrolizumab to site can only be ordered after randomization, every effort should be done to randomize the patient as soon as possible. See Section 9.1 for agent ordering information. If patient is randomized after initiation of 7+3 therapy, the patient should continue to meet all eligibility criteria up to randomization date. Planned stratification factors include 1) age (younger than 65 vs. 65 and older), 2) cytogenetics **by FISH or metaphase karyotype** (presence vs. absence of core binding factor inversions and translocations), and 3) **t- AML or AML arising from prior/antecedent MDS (yes/no)**. All patients will receive cytarabine at 100 mg/m²/day continuous infusion on Days 1-7 and either idarubicin 12 mg/m²/day IV on Days 1-3 or daunorubicin 60 mg/m²/day IV on Days 1-3. A bone marrow biopsy on Day 14 (between Days 14 and 21) will be performed to assess for chemoablation. If patients have evidence of residual leukemia (defined as per institutional practice) in their bone marrow and following assessment by repeat transthoracic echocardiography (TTE) for assessment of ejection fraction, they will receive re-induction 5+2 chemotherapy, which means patients will receive cytarabine at 100 mg/m²/day continuous infusion on Days 1-5 and either idarubicin 12 mg/m²/day IV or daunorubicin 60 mg/m²/day IV on Days 1-2. Anthracycline dosing adjustments may need to be made, per institutional guidelines. Regardless of chemoablation status, on Day 8 of the induction chemotherapy and Q3W (±3 days) thereafter, half of the patients will receive Pembrolizumab (MK-3475) IV (intervention arm). The other half will not receive Pembrolizumab (MK-3475) (control arm). At time of count recovery, defined as platelet count more than 50,000 or neutrophil count more than 500, patients will undergo a bone marrow aspirate/biopsy in order to assess for response and MRD. If there is no count recovery, a bone marrow will have to be performed by day 42. If the bone marrow shows hypoplasia and patient remains without count recovery, a bone marrow will be performed q 2 weeks (+/- 3 days) till there is count recovery or evidence of persistent AML. If patients have a CR or a CRi, patients will continue with consolidation therapy. If patients do not achieve a CR or CRi, they will be taken off study. If Pembrolizumab is discontinued for any reason (after at least one dose of Pembrolizumab, the patient should continue on 7+3 or Re-Induction on study.

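### The microbiome section plans per-patient UniFrac CVs, quartiles built on them and body-site comparisons that two stool samples from one site cannot supply

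*Combined protocol and SAP*

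**What the plan says.** **Planned analysis (Section 10.4.2.8, Gut microbiome).** The section says "Temporal variability will be determined using coefficients of variation (CV") and specifies these as CVs "of the SDI and unweighted and weighted UniFrac distances per patient, with higher values indicative of more variable community composition". It then lists three uses of the measure:

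- "Pairwise differences in temporal variability across body sites will be made using" the Mann–Whitney U test.
- "whereas pairwise differences among response groups performed using" Student's t-test.
- "The population cohort will be divided into quartiles based on CV of the weighted UniFrac distance values or SDI", with the lowest quartile labelled stable, the middle two average and the highest variable.

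**Planned collection.** Section 5.4.6 names baseline and post consolidation cycle 1, and says these "timepoints will use OMNIgene GUT kits". The specimen table (Section 5.1), the biomarker plan (Section 5.8) and the study calendar (Section 12, footnote z) give the same two times. In Section 5.8 stool is the only specimen assigned to the microbiome assay.

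**Who reaches the second sample.** Section 7.1.1 says: "If patients do not achieve a CR or CRi, they will be taken off study". Footnote a of the study calendar repeats the rule before consolidation.

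**The concern.** The analysis text is written for a densely sampled, multi-site microbiome study. A CV over time needs several values per patient, and a comparison across body sites needs at least two sites. The schedule supplies two time points and one site, and the second time point exists only for patients who have already responded to induction.

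The section calls the longitudinal description of microbial shifts its main outcome. If the stated measure cannot be formed, the analyst will have to choose a substitute after the data are in, with no prespecified definition of change.

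**Working it through.** The documents give no sample size, power or precision figure for the microbiome analysis, so there is none to reproduce. The check is a count of what the schedule yields.

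**Inputs**

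- Stool samples per patient: T = 2 at most (Sections 5.1, 5.4.6, 5.8 and 12).
- Body sites sampled for the assay: 1 (Section 5.8).
- Randomized patients: 50, 25 per arm (Section 10.1).
- Induction CR/CRi rate: not fixed for this trial. Assumed 50–80%. For orientation, the cited frontline study of nivolumab with cytarabine and idarubicin reports 72% (23 of 32; Section 2.1.2.2). The background CR rates run from 35–50% in older or adverse-karyotype patients (Section 2.1.1.1) to 70–80% in younger adults (Section 2.3.1.2).

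**1. UniFrac CV.** T samples give T(T−1)/2 within-patient distances. For T = 2 this is 2 × 1 / 2 = 1. The sample SD of one value divides by 1 − 1 = 0 and is undefined; with divisor n it is 0 for everyone. The CV, and any quartile built on it, is therefore unavailable for 50 of 50 patients. For T = 3 there are 3 distances, so three samples are the minimum.

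**2. Body sites.** One site gives 0 pairwise comparisons.

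**3. Shannon CV.** For two values x1 and x2, the SD is |x1 − x2|/√2 and the mean is (x1 + x2)/2, so

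CV = |x1 − x2| / (√2 × mean).

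For example, a fall from 3.0 to 2.0 gives 1/(1.414 × 2.5) = 0.283, and a rise from 2.0 to 3.0 gives the same 0.283. The statistic exists, but it is an absolute before/after difference rescaled by the mean. It does not distinguish loss of diversity from gain.

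**4. Patients without a second sample by design.** 50 × (1 − CR/CRi rate):

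| Assumed induction CR/CRi | No second sample |
|---|---|
| 80% | 10 |
| 72% | 14 |
| 50% | 25 |
| 35% | 32.5, about 33 |

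The 35% row is an extreme: it applies the low end of the older or adverse-karyotype range to the whole trial. Patients in this column have a baseline sample but no measure of change, so change cannot be compared between those with and without CR/CRi after induction.

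**5. Patients with both samples.** Assume also that 80–100% of induction responders complete cycle 1 and provide stool. The paired set is then 50 × 0.50 × 0.80 = 20 to 50 × 0.80 × 1.00 = 40 patients, or 10 to 20 per arm.

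**The case against.** The strongest reply is that the CV paragraph is not the whole microbiome plan. The rest of Section 10.4.2.8 compares microbial shifts between arms and relates diversity to MRD-negative CR after consolidation cycle 1. Part 1 relates baseline biomarkers to response by logistic regression and models change from baseline, naming the gut microbiome. Part 3 compares marker trajectories between arms. All of these work with two time points. This stands. A reader might infer that Objective 1.3.6 cannot be answered; the documents do not support that.

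A second reply is that the quartiles may be based on the Shannon index instead of UniFrac. This also stands: the Shannon route is computable. A reader might go further and call the resulting categories mostly noise, because the 95% normal-theory limits for one patient's SD from two values are 0.45 to 31.9 times the estimate. That interval treats the samples as repeat draws from a stable process, whereas here they bracket induction and a consolidation cycle. The documents give no within- or between-patient variance, so the amount of noise is unknown. The case for replacing the Shannon CV is its loss of direction.

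Third, the section does not define its response groups as induction CR/CRi versus none. MRD status after cycle 1 and later outcomes can still be compared among patients with two samples. Only the induction contrast in change is lost.

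Two other replies fail. Part 2 lists a denser series of biomarker times, but qualifies it as applying where applicable, and no section schedules stool at those times. Reading the UniFrac distances as distances to other patients' samples would make a CV computable, but it would not measure change within a patient, which is how the section describes the metric.

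**Conclusion.** Wrong as written, in a limited part of an exploratory analysis. The per-patient UniFrac CV, the quartiles built on it and the body-site comparison cannot be computed for any patient. These conclusions follow from the schedule alone and need no assumption. The Shannon CV can be computed but only restates an unsigned change.

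Change cannot be compared between induction responders and non-responders. The number of patients affected rests on the assumed CR/CRi rate: 10 to 25 of 50 at 50–80%, 14 at the 72% of a study of a different regimen, and up to about 33 at 35%. Responders who miss the second sample for other reasons would add to this.

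Objective 1.3.6 can still be partly addressed through the other analyses in Section 10.4.2.8. The primary endpoint does not depend on this one. The correction is worth making but minor.

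**What to change.** Amend the text of Section 10.4.2.8:

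1. Delete the UniFrac CVs, the quartiles based on them and the body-site comparison.
2. Define change as the signed paired difference in Shannon index (post cycle 1 minus baseline), in place of its CV, together with the single within-patient weighted and unweighted UniFrac distance.
3. Compare these between arms, and against MRD status and later outcomes, among patients with both samples.
4. Keep baseline diversity and composition against response in all patients with a baseline sample.
5. State that the change analyses are conditional on induction CR/CRi. This is a post-randomization outcome that treatment may affect, since pembrolizumab starts during induction, so the between-arm comparison of change is descriptive.

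The cost is a few sentences and no new samples. If the team wants a true variability measure or the induction contrast, the alternative is to add stool collections, including one at the end of induction. At least three samples per patient are needed for a UniFrac CV, and other sites would have to be sampled for a body-site comparison. That would change the specimen schedule as well as the wording.

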The most reliable biomarker to predict anti-PD-1 Ab therapy includes tumor-infiltrating lymphocytes (TILs). However, further evaluation of TILs subpopulations and their interaction with other TME components will be necessary to identify other response-predictive factors. Compared to a murine model for linear T-cell differentiation, we have had to rely on cross-sectional assessment to define memory T-cell subsets. More than two markers (CD45RA, CCR7) enabled us to delineate memory T-cell compartments (Sallusto *et al.*, 1999). For instance, we simply divide T-cells into four subsets: naïve (CD45RA⁺CCR7⁺), central memory (CD45RA⁻CCR7⁺), effector memory (CD45RA⁻CCR7⁻), and late effector (CD45RA⁺CCR7⁻). The ratio of TCM (CD45RA⁻CCR7⁺) to TEMRA (CD45RA⁺CCR7⁻) and of TEM (CD45RA⁻CCR7⁻) to TEMRA (CD45RA⁺CCR7⁻) will be assessed in BM and peripheral blood using flow cytometry. More recent preclinical data suggest that the frequency of CD8⁺, and CD8⁺/T_{regs} are two important predictive markers for anti-PD-1 therapy (Twyman-Saint Victor *et al.*, 2015). Additionally, this study also demonstrated that exhausted CD8⁺ T-cells defined by the expression of PD-1 and Eomes are reinvigorated, which can be defined by increased Ki67 and Gzmb, following anti-PD-1 and anti-CTLA-4 treatment in a murine model. CD47 is capable of interacting with its receptor signal-regulatory protein alpha (SIRP α) on macrophages to negatively regulate phagocytosis and blockade of CD47 expression results in phagocytosis of red blood cells (RBCs) (Oldenborg *et al.*, 2000). CD47 functions as a ‘don’t eat me’ signal to ensure that autologous cells are not inappropriately phagocytosed. Intriguingly, two recent studies revealed that CD47 is upregulated on leukemia cells and represents an adverse prognosis factor in AML (Jaiswal *et al.*, 2009; Majeti *et al.*, 2009). The ‘eat me’ signal ecto-CRT was shown to correlated inversely with the expression of the ‘don’t eat me’ signal CD47 in AML blasts (Wemeau *et al.*, 2010). We will determine whether other exploratory immune biomarkers predict the response to anti-PD-1 Ab therapy in combination with chemotherapy by assessing immune cell lineage markers as well as functional markers in fresh BM and blood from AML patients using high throughput mass spectrometry (CyTOF).

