10.4.2.3 PD-1 and PD-L1 expression

An association of clinical response with the expression of PD-L1 AML BM cells will be assessed by a Pearson Chi-square test on a 2×2 table of frequencies. The dependent variable will be defined as response (yes *vs.* no), and QIF categories (negative *vs.* positive) will be the independent variables. We will also monitor the dynamic change of PD-L1 expression over the course of treatment and its correlation with clinical response. Longitudinal measurements of PD-L1 will be examined using mixed-effects modeling.

We will assess immune cell markers at different time points of therapy: at baseline (prior to application of 7+3 chemotherapy), at the end of consolidation, after 6 months and 1 year of treatment, and at relapse. We also plan to measure CD47 levels on leukemic blasts prior to and after chemotherapy and Pembrolizumab (MK-3475) administration to see whether CD47 expression levels correlate with responders *vs.* non-responders and whether expression levels change at different times of therapy. Statistical analyses of the frequency of CD8⁺, CD4⁺, FoxP3 T_{regs}, CD8⁺/FoxP3⁺ T_{regs}, T_{CM}/T_{EMRA}, T_{EM}/T_{EMRA}, the percentage of Ki67 and GzmB in PD-1⁺, Eomes⁺ CD8 T-cells to compare changes over time from baseline to several time-points will be performed by using mixed effects modeling with a Benjamini-Hochberg correction to control for false discovery rates.

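### For response, the plan specifies no arm-by-marker analysis, so it cannot separate a marker of pembrolizumab benefit from a general prognostic marker

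*Combined protocol and SAP*

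**What the plan says.** All four analyses are exploratory and, except for the PD-L1 table, sit at the end of Section 10.4.2.8.

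- **Part 1 (response).** "A univariate logistic regression will be selected to assess baseline biomarkers associated with response outcomes". Part 1 also plans mixed models of marker change over time with Benjamini-Hochberg control.
- **PD-L1 (Section 10.4.2.3).** "An association of clinical response with the expression of PD-L1 AML BM cells will be assessed by a Pearson Chi-square test" on a two-by-two table of response by marker category. Arm is not mentioned.
- **Part 2 (survival).** Its heading is "Assess whether baseline biomarkers or the serial measurements of biomarkers are associated with survival outcomes". After the Cox models it adds: "The interaction effects between treatment and biomarkers also will be evaluated".
- **Part 3 (arms).** Its heading is "Compare the biomarkers effects between treatment arms, intensive chemo + pembro vs. intensive chemo only". The baseline analysis begins "The associations between treatment arms and baseline biomarkers will be evaluated using" and names chi-squared or Fisher tests, ANOVA and Mann-Whitney tests. Part 3 then plans mixed models of marker trajectories and says: "The bar plots and trajectory time plots will visually show the differences over time between treatment arms".

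The background sets a predictive aim. Section 2.5.3 says: "We will determine whether other exploratory immune biomarkers predict the response to anti-PD-1 Ab therapy in combination with chemotherapy". Objective 1.3.6 asks for microbiome correlation with response in both treatment settings.

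**The concern.** Asking whether a marker predicts response to pembrolizumab plus chemotherapy means asking whether the marker-response relation differs between arms. The randomised control arm makes that difference estimable. Part 3 carries the heading under which a reader would look for it, but its baseline tests compare marker distributions between randomised groups and contain no outcome. The analyses that do contain response have no term for arm.

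MRD-negative CR/CRi is the primary endpoint, so response is the outcome on which marker findings are most likely to be reported. A marker found in Part 1 could be reported as a guide to who benefits from pembrolizumab when it only marks patients who do better on any intensive chemotherapy. Conversely, a marker whose effect differs in direction between arms could be missed when arm is ignored.

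**Working it through.** **Inputs from the documents.** 1:1 randomisation (Section 7.1.1); 25 patients per arm, 75% versus 50% response, one-sided 0.1, about 71% power (Section 10.1); 92 Olink proteins (Section 10.4.2.4). **Assumptions.** The documents give no marker prevalence and no response rates by marker. Those below are assumed: a binary marker, prevalence 30% to 50%.

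**1. The plan's own figure.** Pooled rate 0.625. Null SE = √(2 × 0.625 × 0.375 / 25) = 0.137; alternative SE = √((0.25 + 0.1875) / 25) = 0.132. Power = Φ((0.25 − 1.282 × 0.137) / 0.132) = 0.713. The stated 71% reproduces and is not in dispute. The plan gives no power for any arm-by-marker analysis of response.

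**2. What each planned analysis contains.**

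| Analysis | Outcome | Arm | Arm × marker |
|---|---|---|---|
| Part 1 baseline logistic model | Response | No (univariate) | No |
| PD-L1 table | Response | Not mentioned | No |
| Part 2 Cox models | Survival | Yes, via the interaction | Yes |
| Part 3 baseline tests | None; marker against arm | Yes | No |
| Part 3 trajectory models and plots | The marker itself | Yes | Not applicable |

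No row has response as the outcome together with an arm-by-marker term.

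**3. Why the response model cannot answer the question.** Take 1:1 arms, 50% prevalence, and response rates as marker-positive / marker-negative.

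- Predictive marker: control 50% / 50%, pembrolizumab 100% / 50%. By marker over both arms: (50 + 100)/2 = 75% and (50 + 50)/2 = 50%. By arm: 50% and 75%.
- Prognostic marker: control 62.5% / 37.5%, pembrolizumab 87.5% / 62.5%. By marker: (62.5 + 87.5)/2 = 75% and (37.5 + 62.5)/2 = 50%. By arm: 50% and 75%.

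The univariate model estimates the same odds ratio in both, (0.75/0.25)/(0.5/0.5) = 3, at any sample size. The arm-by-marker contrast separates them: (100 − 50) − (50 − 50) = 50 points, against (87.5 − 62.5) − (62.5 − 37.5) = 0 points. Here prognostic means equal benefit in percentage points. On the odds-ratio scale the treatment effects in the second case are 7/1.667 = 4.2 and 1.667/0.6 = 2.8, so the scale of the interaction has to be named.

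**4. The Part 3 baseline tests.** Baseline samples are taken before 7+3 and do not depend on assignment. Without adjustment, 92 × 0.05 = 4.6 Olink proteins would be expected to differ by arm at p < 0.05 by chance alone.

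**5. What an interaction term could deliver with 50 patients.** Wald test on the difference of risk differences, variance = Σ p(1 − p)/n over the four arm-by-marker cells, control 50% in both marker groups, prevalence 30% to 50%:

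| Benefit, marker-positive vs marker-negative | Power, one-sided 0.1 | Patients for 80% power |
|---|---|---|
| 25 vs 0 points | 33–36% | 271–314 |
| 40 vs 10 points | 43–45% | 167–184 |
| 45 vs 5 points | 60–62% | 90–96 |

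For the first row at 30% prevalence: variance = 0.4375/7.5 + 0.5/17.5 = 0.087, SE 0.295, power = Φ(0.25/0.295 − 1.282) = 0.33.

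**6. Simulated comparison at one alpha level.** 30% prevalence, before any multiplicity control.

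- One direction: control 50% in both groups; pembrolizumab 64% marker-negative, 100% marker-positive (0.7 × 64 + 0.3 × 100 = 74.8% overall). At two-sided 0.10 the test ignoring arm rejects in about 27% and the interaction test in 29–35% (risk-difference Wald to Firth likelihood ratio). At 0.05: about 16% against 19–21%.
- Opposite directions: the marker moves pembrolizumab response from 60% to 95% and control response from 60% to 25%. Over both arms, (95 + 25)/2 = 60% in marker-positive and 60% in marker-negative, so there is nothing to find when arm is ignored. At 0.10: about 5% against 77%.

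**The case against.** **Part 3 is a valid pharmacodynamic comparison.** Its trajectory models and plots by arm compare what treatment does to the markers, and objective 1.3.2 on immune-cell dynamics supports that reading of the heading. This stands, and those models should stay. It does not rescue the baseline tests, and trajectories with the marker as outcome do not relate markers to response.

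**Interaction is already planned.** A reader might infer that the plan never tests whether a marker predicts benefit. The documents do not support that: Part 2 plans it for survival. The sentence could be meant generally, but it sits under a survival heading directly after Cox models, and Part 1 calls its own model univariate.

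**The documents do not say that arms are pooled.** Correct. For the PD-L1 table the fair statement is that the handling of arm is not specified. A univariate logistic model, however, has no place for arm.

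**The aims are correlational.** The formal objectives mostly speak of association and correlation; prediction comes from the background in Section 2.5.3. This lowers the weight of the point without removing it, because the Part 3 heading itself promises a between-arm comparison.

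**Fifty patients cannot support interactions.** Power is low, as step 5 shows. That argues for estimates with intervals and not for a baseline test that cannot address the question. A reader might also infer a large power gain, for instance by setting a test that ignores arm at 0.05 (about 16%) beside an interaction test at 0.10 (29–35%). At a common level the gain is modest.

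**Conclusion.** The point holds for response only. No written analysis of response contains an arm-by-marker term, and the Part 3 baseline tests do not do what their heading says. The consequence is one of identification: in the worked example, predictive and prognostic markers give the same 75% versus 50% in the response model regardless of sample size.

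The importance is modest. The analyses are exploratory, and no primary or secondary conclusion depends on them. The power gain is small for a one-directional interaction (about 27% to 29–35% at two-sided 0.10) and large only if marker effects reverse between arms (about 5% to 77%), a pattern for which the documents offer no evidence. All marker prevalences and cell rates are assumptions. The identification argument needs none of the power figures.

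**What to change.** - In Part 1, fit for each baseline marker a logistic model of MRD-negative CR/CRi with arm, marker and arm × marker. Because cells will be sparse, a Firth model with penalised likelihood-ratio inference is a reasonable choice; Wald p-values from it are best avoided.
- Report the marker effect within each arm and the difference between arms with an interval. Name the scale, and give response percentages by arm and marker so that the risk-difference scale can be read too.
- Extend the Benjamini-Hochberg control already used in Part 1 to the set of interaction tests.
- In Section 10.4.2.3, show PD-L1 category by response separately for each arm.
- Keep the Part 3 trajectory models and plots. Present the arm by baseline-marker comparisons as a description of balance only, and reword the heading to match.
- If the interaction sentence in Part 2 was meant to cover response, say so in Part 1.

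The cost is analysis wording; no new samples or patients are needed. The drawback is wide intervals for the interaction, which must be labelled hypothesis-generating.
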